COVER PAGE

Study Title: Addressing Health Disparities in Childhood Obesity, One Summer at a Time

Clinical Trials Registration Number: NCT03595332

Date of document: April 15, 2018

Study Protocol

Background

Childhood obesity is one of the most urgent health challenges of our time. Obesity rates of Native American and Hispanic children are far higher than national averages, placing these children at high risk for early mortality, cardiovascular and metabolic conditions including diabetes, depression and overall poor quality of life.¹⁻³ By the 5th grade, approximately 50% of Hispanic and Native children are already overweight, and Native children have type 2 diabetes rates 9 times higher than non-Hispanic Whites.⁴ In our area, obesity rates are highly concentrated: most obese and overweight children are enrolled in 4 of the 10 elementary schools, which include primarily underserved Hispanic and Native American children.

Recent research has further demonstrated that the 'obesity gap' facing minority students is largely due to summer weight gain.⁵⁻⁹ Based on local data, it was confirmed that children in our school district were much more likely to worsen their weight-related health status during the summer than during the schoolyear. However, statewide, only 22% of children participate in summer activities, despite 65% of parents expressing interest.¹⁰ Finally, ages 7 to 11 have been found in national data to see a sharp increase in obesity rates.¹¹ Indeed, locally in 2015, approximately 20% of 7 year-olds are overweight or obese, but 35% of 11-year olds. Thus, we know which populations are at highest risk, at what developmental age changes occur most rapidly (ages 7-11) and that interventions are most needed in the summer, but that this need is not being met.

A modest amount of research has evaluated summer programming, but almost none among Native Americans/Hispanics. In the early 2000s, the CDC developed a 'Summer Scorecard' intervention,¹² a partnership with local businesses to provide children with a 'scorecard' of subsidized or free local activities. The VSS has not been tested among Hispanic and Native American children. Therefore, this study assessed the effectiveness of the VSS among children ages 5-13 in the 4 highest risk schools in the Flagstaff area. Outcomes included body composition (BMI) percentile score, reported physical activity and self-efficacy using survey instruments previously developed and tested by the CDC.

VERB Summer Scorecard Program Description: In 2001, the CDC launched VERB It's What You Do!, a 5-year year national social marketing campaign to increase awareness, improve attitudes, and increase physical activity among 9-13 year olds ("tweens"). The campaign was developed after extensive formative research, grounded in a logic model that shows a pathway to chronic disease reduction,⁴⁵ and tested in 3 follow-ups using a nationally representative sample.¹³⁻¹⁶ The campaign was coordinated with local vendors who provided opportunities to be active. In 2004, the VERB Summer Scorecard (VSS) intervention was developed in 2004. The VSS consists of a 'scorecard' including 24 squares, each representing an activity of at least one hour (see Appendix A for our local version). In collaboration with community partners, children were provided with free or discounted opportunities for a variety of activities. When children attend either an activity at a participating facility or supervised activity at home for a minimum of 60 minutes, they received either a stamp from the community partner or a parent's signature on one of the squares.

Activities:

Each participating child was provided with a scorecard including 24 activities (see Appendix A). Children received 12 free passes to utilize local facilities including a local aquatic center, athletic club (including gym, indoor/outdoor swimming pool, basketball and racquetball courts etc.), climbing gym, ice skating rink and activity center (including bouncy houses, laser tag etc.) and classes offered by a local health program. Other activities could be done on their own and included hiking local trails, going to parks and could be signed off by a parent. Children were instructed to return the card at the end of the summer and receive an incentive prize for returning the card.

Measures:

Demographic variables. Child's age (in years), sex (male or female), ethnicity (American Indian/Alaskan Native, Hispanic, White, Black/African American, Native Hawaiian/Pacific Islander or Two or more), grade level and school membership were collected by the school district. Height and weight were collected at each school during the school day by a community outreach coordinator trained in research quality measurements, supported by the school nurse and volunteers. Children were asked to take shoes and jackets off and items out of their pockets. Height to the nearest quarter inch was measured twice with a Charder HM200P Portstad Portable Stadiometer. Weight was measured to the nearest 0.1 pounds with a Health O Meter 752KL Heavy Duty Remote Display Digital Scale. Children's first weight status was considered their baseline, with $\leq 5^{\text{th}}$ BMI percentile for their age and sex considered underweight, 5^{th} to 85^{th} percentile healthy weight, $\geq 85^{\text{th}}$ percentile overweight and $\geq 95^{\text{th}}$ percentile as having obesity

Behavioral constructs. Health behavior constructs (13 questions) aligned with Social Cognitive Theory were assessed. Key constructs include self-efficacy ("I think I can be physically active even if it is hot or cold outside."), social norms (example: "My friends think that doing physical activity is fun"), and access or barriers to participation in physical activity and summer programs ("There are lots of places near where I live where I can do physical activities").

Reported activity and sedentary behaviors. A total of 8 questions ask about participation in the VERB program, types of activity in the past 7 days and participation in other summer programs. The number of activities reported were counted and compared before and after the intervention.

Recruitment:

Children were recruited directly at each school by research staff in collaboration with school physical education or health and wellness instructors. Recruitment occurred by providing flyers and tables at school events and drop-off/pick up. Parents were provided with a consent form and children with an assent form explaining the risks and benefits. English and Spanish versions were available. Upon completion of both forms, participants were measured and surveyed (see measurements below).

Sample Size calculations: The estimated sample size needed to have sufficient power to detect a moderate effect size (using a Cohen's d of 0.3 as the reference) is 240 children, or 120 per arm. Based on our preliminary data, for each academic year, the average BMI change ranges from 0.35 to 0.55 units, with a standard deviation that varies across ethnic groups and years from 0.80

to 1.00. An example of an effect between two groups or time points that would match a Cohen's d of 0.3 would be one group in which the children on average increases their BMI by 0.5 units, and another group where participants increase their BMI by 0.2 units (0.3 unit difference), with standard deviations of 1.0. These effects (BMI difference of 0.3kgm^2) are just above the mean weighted effect size reported in the most comprehensive and recent meta-analysis on childhood obesity studies of 0.30kg/m^2 .^{9,10} With a two-tailed test and alpha level of 0.05, a sample size of 80 children per arm (a retention rate of 67%) would result in an associated statistical power $\geq 80\%$ to detect intervention effects between arms from one time point to the next. With very similar parameters and sample sizes, prior research has indicated that based on simulation studies,¹⁷ these parameters demonstrated excellent power ($\geq 80\%$) in detecting these size differences.

Institutional Review Board:

All protocol activities were approved by the Institutional Review Board of Northern Arizona University (protocol #1193689) and the Flagstaff Unified School District. Parental consent forms and children assent were attained for each participant.

References:

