COVER PAGE

Study Title: Addressing Health Disparities in Childhood Obesity, One Summer at a Time

Clinical Trials Registration Number: NCT03595332

Date of document: July 14, 2022

Statistical Analysis Plan

The proposed statistical analyses for the current study includes a nested regression model utilizing Generalized Estimating Equations with an exchangeable working correlation matrix to account for the nested data structure of children within schools and families. For all variables, 95% Confidence intervals will be reported (for b in models with a linear response variable and Odds Ratios for models with an ordinal logistic response variable) and a significance level of $p=0.05$ will be used to test hypotheses.

For the primary analysis, we propose to test the difference in Body Mass Index (BMI) Percentile-scores for age and sex based on Centers for Disease Control and Prevention (CDC) criteria from Baseline to 10-weeks using GEE models with a linear response variable. We will test whether the difference is significantly different from zero, adjusting for age (included as a covariate) and sex and ethnicity (included as factors). We will also test whether the immediate intervention group was significantly different from the delayed intervention group by including a variable denoting immediate vs delayed group membership. We will test the null hypothesis that participants in the intervention did not significantly change their BMI Percentile-score.

For the second primary analysis, we will test whether the BMI Percentile from baseline to 10-weeks was significantly different from zero among the highest-risk children, defined as those participants with a baseline BMI Percentile score equal to or greater than the 85th percentile as considered by the Centers for Disease Control and Prevention. GEE models will be used restricting the sample to children with overweight at baseline.

For the first secondary analysis, we propose to test the difference in Body Mass Index Percentile-score from Baseline to 1-year follow-up using GEE models with a linear response variable. We will test whether the difference is significantly different from zero, adjusting for age (included as a covariate) and sex and ethnicity (included as factors). We will test the null hypothesis that participants in the intervention did not significantly change their BMI Percentile-score.

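### Tests of change in the intervention start from the enrolment weight in both groups, so delayed children who are still untreated can contribute waiting time

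*Protocol*

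**What the plan says.** **Baseline.** The only definition is in the protocol, Measures, Demographic variables, where the children's "first weight status was considered their baseline". It makes no distinction by group. The Recruitment section places this measurement at enrolment, once consent and assent were complete: "Upon completion of both forms, participants were measured and surveyed".

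**Groups.** The protocol's sample size section has two arms of 120 children but describes no delayed group. Only the SAP names one, in the primary analysis, where immediate and delayed are compared by "including a variable denoting immediate vs delayed group membership".

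**Tests against zero.** The primary analysis takes the change in BMI percentile "from Baseline to 10-weeks using GEE models with a linear response variable" and asks whether it differs from zero. The stated null is that "participants in the intervention did not significantly change their BMI Percentile-score". The second primary analysis makes the same comparison with zero in children at or above the 85th percentile at baseline. The first secondary analysis makes it at 1 year under the same null. Neither of these two mentions a group term.

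**Not stated.** Neither document gives the delayed group's programme start, a weight shortly before that start, or the way delayed children enter the tests against zero. The nearest wording on timing concerns the activity survey only, again without a schedule by group: "The number of activities reported were counted and compared before and after the intervention".

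**The concern.** For the immediate group, the enrolment weight is also the weight before the programme, so change from it is change over the programme. For the delayed group, the enrolment weight comes before the wait. Ten weeks after enrolment, a child whose programme has not begun has been observed only without treatment. That interval cannot bear on a null about change in the intervention, yet the SAP's wording lets it in.

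The wait is not neutral. The protocol's Background says that local children's weight status worsens more in summer than in the school year, so an untreated summer is where worsening is expected. Mixing it with treated time moves the result of the first test that the SAP lists, and a reader would take that result as what happened to children during the programme.

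The 1-year test has the same weakness. A delayed child may be untreated for all or part of that year, and no group term is mentioned to separate the two groups.

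**Working it through.** **1. Who enters the primary analysis, and over which interval.**
- The SAP fits a group variable, so delayed children are in at least that model.
- The window runs from baseline to 10 weeks, and baseline is the enrolment weight for everyone.
- The comparison with the delayed group isolates the programme only if that group is still untreated at 10 weeks. I assume that it is.
- On these three points, the delayed group's change from baseline to 10 weeks is waiting time, while the null speaks of change in the intervention.

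**2. Inputs for an illustration** (protocol, sample size section):
- change of +0.5 BMI units in one group and +0.2 in the other, read here as untreated and treated;
- SD 1.0;
- 240 children, 120 per arm.

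The protocol's own figures reproduce: 0.5 − 0.2 = 0.3; 0.3 / 1.0 = 0.3, its Cohen's d; 240 / 2 = 120.

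**3. Pooled change.** Let w be the delayed share of the analysed children.

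Pooled change = (1 − w) × 0.2 + w × 0.5

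| Delayed share w | Immediate-group change | Pooled change | Delayed minus immediate |
|---|---|---|---|
| 0.25 | 0.20 | 0.75 × 0.2 + 0.25 × 0.5 = 0.275 | 0.30 |
| 0.50 | 0.20 | 0.50 × 0.2 + 0.50 × 0.5 = 0.35 | 0.30 |
| 0.75 | 0.20 | 0.25 × 0.2 + 0.75 × 0.5 = 0.425 | 0.30 |

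With equal arms, the pooled figure exceeds the treated group's own change by 0.35 − 0.20 = 0.15. Measured against the untreated +0.5, it shows a benefit of 0.5 − 0.35 = 0.15, half of the 0.3 that the immediate group shows. The comparison between groups is unaffected.

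**4. What the group variable does to the test against zero.** Write change = a + b × group, ignore the covariates and take equal arms. The constant a, which would be tested against zero, depends on coding:
- immediate as reference: a = 0.20;
- groups coded −½ and +½: a = (0.2 + 0.5) / 2 = 0.35;
- delayed as reference: a = 0.50;
- no group term: a = 0.35.

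Only the first is change in treated children. The SAP does not state the coding, or whether the test against zero uses the same model as the group comparison.

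**5. Scale.** The figures are raw BMI units, whereas the endpoint is BMI percentile for age and sex, which already allows for age-expected change. The sizes do not transfer. The direction does: on any scale, a pooled mean lies between the treated and untreated means.

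**The case against.** The strongest reply is that this is a gap in the description and not an error. The sponsor may have left delayed children out of the tests against zero, since the null concerns children in the intervention, or may have weighed them again before their own programme. With the immediate group as reference, the primary test against zero would be correct as it stands. The study is powered between arms, and for that comparison the enrolment weight, and 85th-percentile status at enrolment, are the right references in both groups if the delayed group is untreated at 10 weeks.

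The last point stands in full and limits the concern to the tests against zero. The others describe ways in which the analysis could be sound, but the SAP states none of them, and its literal text admits untreated time.

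A reader might also infer more than the documents support:

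- *That the delayed group has no weight before its programme, or that its programme period cannot be analysed.* The enrolment weight does precede a delayed start. What is unspecified is a second weight close to that start, and silence does not show that none was taken.
- *That the delayed group's change spans wait plus programme and so carries the 0.35 to 0.55 units of academic-year BMI change given in the protocol.* After a long wait, that interval would contradict the SAP's 10-week window. Those figures are also raw BMI over an academic year, and cannot be carried onto a percentile normed for age and sex.

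**Conclusion.** The concern holds in limited form. One enrolment baseline serves both groups, the delayed programme's start is undefined, and the SAP words its tests against zero as change in the intervention without excluding time before the programme. Followed literally, that gives a wrong answer to the question asked, and not only an incomplete description.

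In the protocol's example, the pooled change is 0.35 against 0.20 in the immediate group, and ranges from 0.275 to 0.425 as the delayed share goes from 25% to 75%. This rests on three assumptions: the delayed group is untreated at 10 weeks, its children are pooled in the test against zero, and, for the 0.35, the arms are equal. It shows direction, not size on the percentile scale.

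The immediate-versus-delayed comparison at 10 weeks is not affected. The primary test, the test in children at or above the 85th percentile, and the 1-year test, each against zero, are.

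**What to change.** Amend the SAP as follows.

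1. State when the delayed group's programme starts, and which weights were taken shortly before and after it.
2. For immediate versus delayed at 10 weeks, keep the enrolment weight and 85th-percentile status at enrolment.
3. For any test of change in the intervention, exclude all time before a child's own programme start. Use the immediate group from enrolment. Add a delayed child only if there is a weight shortly before and after that child's own programme, with the earlier of the two as reference and as the basis for 85th-percentile status.
4. State the model and the coding of the group variable for each test against zero.
5. Do not interpret the 1-year test against zero as an intervention effect for delayed children who are untreated for all or part of that year.

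The cost is SAP wording and one derived variable for the reference weight. The sample for within-programme change becomes smaller. The planned 1-year weight would not by itself bring the delayed group in: if their programme starts at about 1 year, neither document lists a later weight to close the interval. Without such a weight, the within-programme analysis rests on the immediate group alone, and the report should say so.

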Appendix A: Scorecard

SUMMER SCORECARD

June-August 6

For each activity you complete:

1. Write the date.
2. Have your parent or guardian initial the box or get a Fit Kids stamp at the front desk when you check in at the Aquaplex, Cabin Fever, Flagstaff Athletic Club (FAC) or Jay Lively Activity Center.

Each activity is worth three points. Earn bonus points for completing more activities!

- **Complete 12 for 40 points (four bonus pts.)**
- **Complete 18 for 60 points (six bonus pts.)**
- **Complete all 24 for 80 points (eight bonus pts.)**

Activities must be completed by Sunday, Aug. 6. Turn in your Scorecard to Fit Kids staff during the month of August to receive your points.

Fit Kids Summer Series Bowling
	
Fit Kids Summer Series Running Club
	
Swim and play at FAC
	
Hike Fat Man's Loop 3 bonus points for a picture along the trail!
	BONUS

Family swim at FAC East 2 bonus points for a family picture!
	
Hike one of the Campbell Mesa Trails
	
Ride your bike for 60 minutes
	
Play a sport for 60 minutes If you're on a team, practice or games count!
	

Ice skating at Jay Lively
	
Your choice 60 minutes of activity
	
CrossFit Kids workout
	
Explore the lava tubes 3 bonus points for a picture in the cave!
	

Walk the big loop at Buffalo Park 2 bonus points for a picture with the buffalo!
	
Go to: NEW ROOTS FLAGSTAFF, AZ Summer Series Class
	
Flagstaff Community Market Local flavor at root level!
	
Family swim at FAC East
	

Play a sport for 60 minutes If you're on a team, practice or games count!
	
Hike Sedona's Red Rocks 3 bonus points for a picture along the trail!
	
Swim and play at Flagstaff Aquaplex
	
5K Walk/Run 2 bonus points for participating in the Machine Solutions Run for Kids on Aug. 5. Fit Kids get free entry!
	

CABIN Fever Laster tag, climbing and inflatables
	
Hike Mt. Humphreys 10 bonus points for a picture at the summit!
	
Your choice 60 minutes of activity
	
Round of Disc Golf

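### Reported physical activity has only an uncontrolled before/after comparison and no SAP analysis, so a change in the count cannot be attributed to the programme

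*Protocol*

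**What the plan says.** The Protocol's Background names the outcome: "Outcomes included body composition (BMI) percentile score, reported physical activity and self-efficacy". Under Measures, the paragraph on reported activity and sedentary behaviours describes eight questions covering "participation in the VERB program, types of activity in the past 7 days and participation in other summer programs". It closes with the only comparison stated for this outcome: "The number of activities reported were counted and compared before and after the intervention". It does not say which of the eight questions enter the count, when the follow-up survey is given, or whether groups are compared.

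On timing, the scorecard in Appendix A is headed June to 6 August and states "Activities must be completed by Sunday, Aug. 6". The Recruitment section says that children were recruited at their schools and were measured and surveyed once consent and assent forms were complete.

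The SAP analyses BMI percentile (at 10 weeks, at 10 weeks in children at or above the 85th percentile at baseline, and at 1 year) and self-efficacy. Reported activity does not appear. The primary BMI analysis covers change "from Baseline to 10-weeks using GEE models with a linear response variable" and tests immediate against delayed intervention "by including a variable denoting immediate vs delayed group membership". No other analysis in the SAP mentions that variable.

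**The concern.** A before/after comparison in one group measures everything that changed between the two surveys. The study's own rationale is that summer differs from the school year for these children. A survey completed at school before June and another around the end of the scorecard period would differ in season, daylight, school physical education and free time, as well as in the programme. The comparison cannot separate these influences.

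The bias could go either way. If children are more active in summer whatever they are offered, an ineffective programme looks effective. If they lose school-based activity, a useful programme looks useless. At stake is whether the study can say anything about the programme's effect on the behaviour it is meant to change.

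**Working it through.** **No figure to reproduce.** The documents give no effect size, SD, sample size or power for the activity count. What follows shows how the two comparisons behave. It does not estimate the bias in this trial.

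**What each comparison estimates.** Let S be the mean change in count due to season and school schedule, and P the mean change due to the programme.

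- Before/after in the immediate group: S + P.
- Immediate minus delayed at a concurrent follow-up, before the delayed group starts: (S + P) − S = P, provided S is the same in both groups.

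**Inputs.** n = 80 is the retained number per arm in the Protocol's sample size section, and 160 is both arms together. Alpha is 0.05 (SAP), taken as two-sided as in that section. The shift δ = S/SD of the change is assumed, from 0 to 0.5, and P = 0. Children are treated as independent, so clustering by school and family is ignored.

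**Formula.** For a two-sided one-sample z-test, the rejection probability is 1 − Φ(1.96 − δ√n) + Φ(−1.96 − δ√n).

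Example: n = 80 and δ = 0.2 give δ√n = 1.789, and 1 − Φ(0.171) + Φ(−3.749) = 0.432.

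| Assumed shift δ | Before/after, n = 80 | Before/after, n = 160 |
|---|---|---|
| 0 | 5.0% | 5.0% |
| 0.1 | 14.5% | 24.4% |
| 0.2 | 43.2% | 71.6% |
| 0.3 | 76.5% | 96.7% |
| 0.5 | 99.4% | about 100% |

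A larger sample makes the false finding more likely, because the test then detects S more reliably.

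**Between-group check.** In 20,000 simulated trials with 80 per arm, the same shift in both arms and no programme effect, a two-sample t-test on the change rejected in 5.1%, 5.1% and 5.0% of trials at shifts of 0, 0.2 and 0.5 SD. The common shift cancels.

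**Opposite direction.** The test is two-sided, so a seasonal fall of the same size gives the same rejection rates. If P = +0.3 SD and S = −0.3 SD, the expected before/after change is 0, and a real effect is found only 5% of the time. The expected between-group difference is still 0.3 SD.

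**Price in precision.** The standard error of one group's mean change is SD/√80 = 0.112 SD. For the difference between two groups of 80 it is SD × √(2/80) = 0.158 SD, larger by √2 = 1.41. For a true 0.3 SD, power is 76.5% for the one-group test and 47.5% for the two-group test. The 76.5% is power to detect S + P, not P.

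**The case against.** The strongest reply is that the documents settle less about timing than the argument needs. The 10-week point is given for BMI percentile and self-efficacy, not for the activity survey. If follow-up surveys were done at school, as enrolment was, both seven-day recalls might fall in term time and much of the school-schedule shift would disappear. The Protocol's sentence also speaks of before and after the intervention, not the summer. This stands as a limit on how large the bias is. It does not rescue the comparison: a one-group change still has no concurrent reference, and the documents do not show that the two recalls fall in comparable weeks.

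It is also fair to say that this is not a primary outcome, that the Protocol's sentence names no test, and that the later SAP attaches no hypothesis to it. That lowers the priority of the point.

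Two stronger readings are tempting and are not supported:

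- A reader might infer that the count is inflated by the questions on VERB and other summer-programme participation. A participation question could hardly be answered yes before the programme begins, so counting it would raise the later total mechanically. But nothing says these questions enter the count, and the more natural reading is that activity types are counted. Activity done within the programme is also part of the intended effect, not in itself an artefact.
- A reader might infer that a delayed group surveyed at the same times is available and simply unused. The SAP's 10-week group comparison for BMI suggests a concurrent visit, but neither document gives the delayed group's schedule for the activity survey.

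**Conclusion.** The point holds for attribution. A named outcome has one stated comparison, that comparison is uncontrolled, and the SAP does not replace it although the trial has two arms and a group variable. As written, a before/after change in reported activity, up or down, cannot be ascribed to the programme.

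The size of the bias cannot be computed from the documents. The rejection rates above rest on an assumed shift and show only that modest shifts are enough to mislead. That a between-group comparison removes the problem rests on two assumptions: that both groups were surveyed at the same follow-up, and that season acts equally on both. The documents do not say how the groups were formed, so the second also needs a supporting statement.

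The change should be made, but it concerns a supporting outcome and does not affect the primary BMI analysis.

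**What to change.** 1. Confirm and state when the activity survey was given at baseline and follow-up in each group, and whether the delayed group's follow-up came before its own programme.
2. If the surveys were concurrent, add to the SAP a comparison of the follow-up seven-day activity count between immediate and delayed groups. Use the GEE framework already planned, with baseline count and age as covariates and sex and ethnicity as factors, and report the group coefficient with its 95% confidence interval.
3. State that only the seven-day activity-type items form the count. Report the VERB and other summer-programme participation items separately, as exposure.
4. Report before/after change within each group as descriptive only, without a test presented as evidence of effect.
5. If the surveys were not concurrent, say so, keep the outcome descriptive and make no claim of a programme effect on activity.

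If both groups have the data, the cost is SAP wording and one extra model. The downside is less precision than a one-group test: a standard error about 1.41 times as large at equal group sizes before baseline adjustment, which may recover part of it.

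### The sample-size rationale is in academic-year BMI units and is not translated to 10-week BMI percentile change, and the stated power fails on its own inputs (about 47%, not at least 80%)

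*Protocol*

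**What the plan says.** The Protocol (Sample Size calculations) takes a standardised effect as its starting point: "using a Cohen's d of 0.3 as the reference) is 240 children, or 120 per arm". Its support for that effect is in kg/m2. The preliminary data are given by school year: "for each academic year, the average BMI change ranges from 0.35 to 0.55 units". Their SD is put at between 0.80 and 1.00, depending on ethnic group and year. The worked example contrasts a gain of 0.5 with a group whose children "increase their BMI by 0.2 units (0.3 unit difference), with standard deviations of 1.0". The external benchmark, a meta-analysis mean of 0.30, is also in kg/m2.

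The power claim is for 80 children analysed in each arm (67% retention), two-sided at 0.05. Power is put at 80% or more "to detect intervention effects between arms from one time point to the next".

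The SAP's primary analysis reads "we propose to test the difference in Body Mass Index (BMI) Percentile-scores for age and sex" by CDC criteria, from baseline to 10 weeks. It uses GEE with adjustment for age, sex and ethnicity, and it includes an immediate-versus-delayed group term. The Protocol's Background also names the percentile score as the body-composition outcome.

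**The concern.** Two things differ between the rationale and the test. The scale moves from kg/m2 to an age- and sex-specific percentile. The period moves from an academic year to 10 weeks, which the Appendix A scorecard places in June to early August. The period matters here because the Background bases the study on summer and school year behaving differently. Without an SD, an expected change or a target difference for 10-week percentile change, a reader cannot tell what the trial could detect on its primary endpoint.

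The power figure also looks too high for d = 0.3 with 80 per arm, whatever the scale. What is at stake is how to read a non-significant between-group result. A reader who trusts the 80% figure would take such a result as evidence against a moderate effect, although the trial had roughly an even chance of missing one.

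**Working it through.** **Inputs (Protocol, Sample Size calculations):** d = 0.3 (difference 0.3, SD 1.0); two-sided alpha 0.05; 120 per arm planned; 80 per arm analysed (80/120 = 66.7%, the stated retention); between-arm contrast of change.

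**Step 1: try to reproduce the stated power.** For two equal groups of n, power ≈ Φ(d·√(n/2) − 1.96).

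- 80 per arm: 0.3 × √40 = 1.897; 1.897 − 1.96 = −0.063; Φ = 47.5% (t-test 47.1%).
- 120 per arm: 0.3 × √60 = 2.324; 2.324 − 1.96 = 0.364; Φ = 64.2% (t-test 63.9%).
- Analysed n needed for 80%: 2 × (1.96 + 0.8416)² / 0.3² = 174.4, so 175 per arm. At the stated retention this is 175/(80/120) = 262.5, so 263 per arm and 526 in total.

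The stated figure of at least 80% is not reproduced.

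**Step 2: look for a reading that rescues it at 80 per arm.**

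| Reading | Power |
|---|---|
| SD 0.8 (d = 0.3/0.8 = 0.375), two-sided | 66.0% |
| SD 1.0, one-sided | 60.0% |
| SD 0.8, one-sided | 76.6% |

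No between-arm reading of the stated inputs reaches 80% with 80 per arm. SD 0.8 with 120 per arm gives 82.8%, but that means d = 0.375 and no attrition. Adjustment for baseline BMI would need a correlation of about 0.74. That figure is not stated, the SD is already that of a change, and the SAP's listed covariates do not include baseline BMI.

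**Step 3: what these numbers can detect on any scale.** Difference for 80% power = 2.8016 × √(2/n) SD.

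- 80 per arm: 2.8016 × 0.1581 = 0.443 SD (t-test 0.446).
- 120 per arm: 2.8016 × 0.1291 = 0.362 SD (t-test 0.363).

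**Step 4: put this on the percentile scale.** The documents give no SD for 10-week percentile change, so the SDs below are assumptions. Detectable difference = t-test multiple × SD.

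| Assumed SD (points) | 80 per arm | 120 per arm |
|---|---|---|
| 5 | 2.2 | 1.8 |
| 8 | 3.6 | 2.9 |
| 10 | 4.5 | 3.6 |
| 15 | 6.7 | 5.4 |

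**Step 5: does d carry over to percentiles? (illustration only)** Assume normal baseline BMI z-scores (mean 0.6 to 1.04, SD 1.0 to 1.1), with an effect and a spread of change that are uniform in z at d = 0.30. Simulation then gives d of about 0.25 to 0.27 in percentile points, because percentiles compress change in heavier children. Power at 80 per arm would be Φ(0.25 × 6.325 − 1.96) = 35% to Φ(0.27 × 6.325 − 1.96) = 40%. This converts z-scores to percentiles, whereas the Protocol's d is in kg/m2. It shows that d need not carry over, and it does not estimate the trial's actual loss.

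None of these figures allows for clustering. The SAP models children within schools and families, but the sample-size section gives no intraclass correlation or design effect.

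**The case against.** The strongest defence is that N rests on a unitless d. The BMI-unit case is offered as an example, and d = 0.3 could equally be a target for percentile change. That stands as far as it goes, and it is why the mismatch does not prove that the effect size is wrong for the primary endpoint. But the only evidence offered that 0.3 is realistic is in other units, with its means and SDs from another period, so for the tested endpoint d = 0.3 is unsupported.

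A reader might infer more: that the 0.3-unit effect should be scaled down from a school year to 10 weeks, leaving power very low. The documents do not support that. The 0.5 versus 0.2 example and the meta-analysis benchmark carry no stated period; only the preliminary means and SDs are tied to the academic year. No accrual rate is given either, and the answer depends wholly on the one assumed. Even accrual over an assumed 36 to 40 weeks gives about 7 to 17% power at 80 per arm. Three times that rate, with the SD shrinking by the square root of time, gives about 81 to 85%. A range that wide says nothing about a shortfall.

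On the power claim, two defences are possible. First, the SAP also tests change against zero, and at d = 0.3 a one-sample test would have 75.5% power with 80 children or 96.5% with 160 pooled. But the Protocol attaches its 80% to the contrast between arms. Second, the Protocol cites simulations from a similar trial. It does not report the design features or correlations behind them, so they cannot be reconciled with the two-arm calculation.

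Finally, the Protocol is written in the past tense and the SAP is dated July 2022, so N probably cannot change. That is fair, and it limits the remedy to restatement.

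**Conclusion.** The point holds in two parts, with different certainty.

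- **Mismatch of scale and period:** certain as a matter of text. The consequence is that d = 0.3 and its power are not shown to apply to 10-week percentile change. It cannot be said that they are inapplicable, nor how much power is lost; the 0.25 to 0.27 illustration depends on assumptions outside the documents.
- **Stated power:** wrong on its own inputs. It is about 47% with 80 per arm and about 64% with 120, assuming a simple two-arm comparison of independent children. The trial has 80% power only for differences of about 0.45 SD (80 per arm) or 0.36 SD (120 per arm). Positive clustering among children in the same arm would raise those thresholds if arms were formed by school or family.

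The two parts should not be added together as separate power losses. Both need repair: correcting the scale alone leaves the arithmetic wrong, and correcting the arithmetic alone leaves a figure for a different variable.

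**What to change.** Keep N and change the text.

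1. From the preliminary school data, take the SD of spring-to-fall (about 10-week) change in BMI percentile. The Background's local comparison of summer with school year suggests such data may exist. If they do not, state an assumed SD range.
2. Replace the claim of at least 80% with the recomputed power. Give the between-arm difference in percentile points detectable at 80% power with 80 and with 120 per arm, and say whether clustering is allowed for.
3. Keep the BMI-unit example but label it as the original rationale for N, not as support for the primary endpoint.

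The cost is one run of existing data, if available, and a few sentences. The downside is that the stated power becomes less favourable.
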